##### **9.2.2.7.1. Injection Site Reactions**

Injection site reactions will be collected on the eCRF separate from the hypersensitivity reaction eCRF. At the time of AE occurrence in the LY3298176 group, samples will be collected for measurement of LY3298176 ADA and LY3298176 concentration.

##### **9.2.2.7.2. Anti-Drug Antibodies**

The occurrence of ADA formation will be assessed as outlined in Section 9.4.3.

**9.2.2.8. Diabetic Retinopathy Complications**

Dilated retinal fundoscopic examination will be performed by a qualified eye care professional (ophthalmologist or optometrist) for all patients between Visit 2 and Visit 3 to exclude patients with proliferative retinopathy and/or maculopathy. The results from this examination will be recorded on a specific retinopathy eCRF as a baseline measure of retinopathy.

A follow-up dilated fundoscopic examination should be performed when clinically indicated by any AE suspected of worsening retinopathy, and the findings should be recorded on the retinopathy eCRF.

**9.2.2.9. Hepatobiliary Disorders**

All events of TE biliary colic, cholecystitis, or other suspected events related to gallbladder disease should be evaluated and additional diagnostic tests performed, as needed. In cases of elevated liver markers, hepatic monitoring should be initiated as outlined in Section 9.4.5.1 and Appendix 4.

**9.2.2.10. Severe Gastrointestinal Adverse Events**

LY3298176 may cause severe GI AEs, such as nausea, vomiting, and diarrhea. Information about severe GI AEs as well as antiemetic/antidiarrheal use will be collected in the eCRF/AE form. For detailed information concerning the management of GI AEs, please refer to Section 7.7.1.

**9.2.2.11. Acute Renal Events**

Renal safety will be assessed based on repeated renal functional assessment as well as assessment of AEs suggestive of acute or worsening of chronic renal failure. Gastrointestinal AEs have been reported with LY3298176, including nausea, diarrhea, and vomiting. These are consistent with other GLP-1 receptor agonists (Aroda and Ratner 2011). The events may lead to dehydration, which could cause a deterioration in renal function, including acute renal failure. Patients should be advised to notify investigators in case of severe nausea, frequent vomiting, or symptoms of dehydration.

**9.2.2.12. Metabolic Acidosis, Including Diabetic Ketoacidosis**

Ketoacidosis, a serious life-threatening condition requiring urgent hospitalization, has been reported rarely in patients with T2DM. Patients who present with signs and symptoms consistent with severe metabolic acidosis should be assessed for ketoacidosis regardless of presenting BG levels, as ketoacidosis may be present even if BG levels are less than 250 mg/dL. If ketoacidosis is suspected, SGLT-2i should be discontinued (if used), patient should be evaluated, and prompt treatment should be instituted. Treatment of ketoacidosis may require insulin, fluid and carbohydrate replacement.

Lactic acidosis has been reported rarely in patients with T2DM associated with use of metformin, excessive alcohol intake and decrease renal function. Routine bicarbonate assessment will be performed during the course of the study. If lactic acidosis is suspected, metformin should be temporarily discontinued until the resolution of the event.

**9.2.2.13. Amputation/Peripheral Revascularization**

All cases of amputation and peripheral revascularization should be reported as an AE.

#### **9.2.2.14. Major Depressive Disorder/Suicidal Ideation**

The prevalence of depressive symptoms and disorders is increased in patients with T1DM or T2DM (ADA Guideline, 2017). Any AE of major depressive disorder or suicidal ideation should be reported.

#### **9.2.3. Complaint Handling**

Lilly collects product complaints on investigational products and drug delivery systems used in clinical studies in order to ensure the safety of study participants, monitor quality, and to facilitate process and product improvements.

Patients will be instructed to contact the investigator as soon as possible if he or she has a complaint or problem with the investigational product so that the situation can be assessed.

### **9.3. Treatment of Overdose**

Study drug overdose (more than the specified number of injections) will be reported as an AE. In the event of overdose, refer to the IB for LY3298176 and/or Product Label for insulin degludec (Degludec USPI, 2015 [WWW]).

### **9.4. Safety**

#### **9.4.1. Electrocardiograms**

For each patient, electrocardiograms (ECGs) should be collected according to the Schedule of Activities (Section 2). Electrocardiograms should be recorded according to the study-specific recommendations included in the Manual of Operations for the study.

Electrocardiograms will initially be interpreted by a qualified physician (the investigator or qualified designee) at the site as soon after the time of ECG collection as possible, and ideally while the patient is still present, for immediate subject management, should any clinically relevant findings be identified. Any clinically significant findings from ECGs that result in a diagnosis and that occur after the patient receives the first dose of the investigational treatment should be reported to Lilly or its designee as an AE via the eCRF.

All digital ECGs will be obtained using centrally provided ECG machines and will be electronically transmitted to a designated central ECG laboratory. The central ECG laboratory will perform a basic quality control check (for example, demographics and study details) and then store the ECGs in a database. At a future time, the stored ECG data may be overread by a cardiologist at the central ECG laboratory for further evaluation of machine-read measurements or to meet regulatory requirements. The machine-read ECG intervals and heart rate may be used for data analysis and report-writing purposes, unless a cardiologist overreading of the ECGs is conducted prior to completion of the final study report (in which case, the overread data would be used).

#### **9.4.2. Vital Signs**

For each patient, vital signs measurements should be conducted according to the Schedule of Activities (Section 2) and following the study-specific recommendations included in.

Any clinically significant findings from vital signs measurement that result in a diagnosis and that occur after the patient receives the first dose of study treatment should be reported to Lilly or its designee as an AE via eCRF.

### **9.4.3. Laboratory Tests**

For each patient, laboratory tests detailed in ([Appendix 2](#)) should be conducted according to the Schedule of Activities (Section [2](#)).

With the exception of laboratory test results that may unblind the study (if applicable), Lilly or its designee will provide the investigator with the results of laboratory tests analyzed by a central vendor, if a central vendor is used for the clinical trial.

Any clinically significant findings from laboratory tests that result in a diagnosis and that occur after the patient receives the first dose of investigational product should be reported to Lilly or its designee as an AE via eCRF.

### **9.4.4. Immunogenicity Assessments**

Where local regulations and ERBs allow, blood samples for immunogenicity testing will be collected to determine antibody production against LY3298176 as specified in the Schedule of Activities (Section [2](#)).

At the visits and times specified in the Schedule of Activities (Section [2](#)), venous blood samples will be collected to determine antibody production against the LY3298176. To interpret the results of immunogenicity, a PK sample will be collected at the same time points as the immunogenicity sample. All samples for immunogenicity should be taken predose when applicable and possible. In the event of drug hypersensitivity reactions (immediate or non-immediate), additional samples will be collected (including ADA, PK, and exploratory immune safety sample) as close to the onset of the event as possible, at the resolution of the event, and 30 days following the onset of the event. Instructions for the collection and handling of blood samples will be provided by the sponsor. Sample collected at Visit 801 will assess immunogenicity at washout of LY3298176 (5 half-lives post end of treatment).

Treatment-emergent ADAs are defined in Section [10.3.5](#).

Samples with LY3298176 ADA detected will be titered and evaluated for their ability to neutralize the activity of assigned treatment (LY3298176-neutralizing antibodies). Samples with LY3298176 ADA detected will also be tested for cross-reactive binding to native GIP and GLP-1, and, if such is detected, then for neutralizing antibodies against native GIP and GLP-1, respectively.

Samples will be retained for a maximum of 15 years after the last patient visit, or for a shorter period if local regulations and ethical review boards (ERBs) allow, at a facility selected by the sponsor. The duration allows the sponsor to respond to future regulatory requests related to LY3298176. Any samples remaining after 15 years will be destroyed.

### **9.4.5. Safety Monitoring**

Lilly will periodically review evolving aggregate safety data within the study by appropriate methods.

#### **9.4.5.1. Hepatic Safety Monitoring**

If a study patient experiences elevated ALT  $\geq 3X$  ULN, ALP  $\geq 2X$  ULN, or elevated TBL  $\geq 2X$  ULN, liver testing ([Appendix 4](#)) should be repeated within 3 to 5 days including ALT, AST, ALP, TBL, direct bilirubin, gamma-glutamyl transferase, and creatine kinase to confirm the abnormality and to determine if it is increasing or decreasing. If the abnormality persists or worsens, clinical and laboratory monitoring should be initiated by the investigator and in consultation with the study medical monitor. Monitoring of ALT, AST, TBL, and ALP should continue until levels normalize or return to approximate baseline levels.

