## 8. Discontinuation Criteria

### 8.1. Discontinuation from Study Treatment

#### 8.1.1. *Permanent Discontinuation from Study Treatment*

Possible reasons leading to permanent discontinuation of investigational product:

- **Patient Decision**
  - The patient requests to discontinue investigational product.
- **Discontinuation due to a hepatic event or liver test abnormality.** Patients who are discontinued from investigational product due to a hepatic event or liver test abnormality should have additional hepatic safety data collected via the eCRF.

Discontinuation of the investigational product for abnormal liver tests **should be** considered by the investigator when a patient meets one of the following conditions after consultation with the Lilly-designated medical monitor:

- ALT or aspartate aminotransferase (AST) >8X ULN
- ALT or AST >5X ULN for more than 2 weeks
- ALT or AST >3X ULN and total bilirubin level (TBL) >2X ULN or international normalized ratio (INR) >1.5
- ALT or AST >3X ULN with the appearance of fatigue, nausea, vomiting, right upper-quadrant pain or tenderness, fever, rash, and/or eosinophilia (>5%)
- alkaline phosphatase (ALP) >3X ULN
- ALP >2.5X ULN and TBL >2X ULN
- ALP >2.5X ULN with the appearance of fatigue, nausea, vomiting, right quadrant pain or tenderness, fever, rash, and/or eosinophilia (>5%)

In addition, patients will be discontinued from the investigational product in the following circumstances:

- If a patient is inadvertently enrolled and it is determined that continued treatment with study drug would not be medically appropriate, see Section 8.1.3
- Acute or chronic pancreatitis
- If a patient is diagnosed with MTC after randomization, or has a postrandomization calcitonin value  $\geq 35$  ng/L that has increased at least 50% over baseline
- If a patient is diagnosed with an active or untreated malignancy (other than basal or squamous cell skin cancer, in situ carcinomas of the cervix, or in situ prostate cancer) after randomization
- Any significant study drug-related hypersensitivity reaction

- Any other TEAE, SAE, or clinically significant laboratory value for which the investigator believes that permanent study drug discontinuation is the appropriate measure to be taken
- If female patient becomes pregnant
- If a patient is diagnosed with T1DM

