### **9.2. Adverse Events**

Investigators are responsible for monitoring the safety of patients who have entered this study and for alerting Lilly or its designee to any event that seems unusual, even if this event may be considered an unanticipated benefit to the patient.

The investigator is responsible for the appropriate medical care of patients during the study.

Investigators must document their review of each laboratory safety report.

The investigator remains responsible for following, through an appropriate health care option, AEs that are serious or otherwise medically important, considered related to the investigational product or the study, or that caused the patient to discontinue the investigational product before completing the study. The patient should be followed until the event resolves or stabilizes with appropriate diagnostic evaluation. For events that are not anticipated to resolve or stabilize, the patient should be followed until the treating physician (in consultation with the sponsor) determines that appropriate follow-up has been completed. The frequency of follow-up evaluations of the AE is left to the discretion of the investigator.

Lack of drug effect is not an AE in clinical studies, because the purpose of the clinical study is to establish treatment effect.

After the ICF is signed, study site personnel will record via the eCRF, the occurrence and nature of each patient's preexisting conditions, including clinically significant signs and symptoms of the disease under treatment in the study. In addition, site personnel will record any change in the condition(s) and any new conditions as AEs. For each AE, the onset and duration, the seriousness and severity, and the actions taken with respect to study treatment will be recorded. Investigators should record their assessment of the potential relatedness of each AE to protocol procedure, investigational product, via electronic case report form (eCRF).

Procedures and assessments performed prior to Visit 3 are considered screening procedures. The results of these procedures and assessments should be considered pre-existing conditions and should be reported as medical history or concomitant illness.

The investigator will interpret and document whether or not an AE has a reasonable possibility of being related to study treatment, study device, or a study procedure, taking into account the disease, concomitant treatment or pathologies.

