#### **Hepatic Safety Data Collection**

Additional safety data should be collected via the eCRF if 1 or more of the following conditions occur:

- elevation of serum ALT to  $\geq 5X$  ULN on 2 or more consecutive blood tests
- elevated serum TBL to  $\geq 2X$  ULN (except for cases of known Gilbert's syndrome)
- elevation of serum ALP to  $\geq 2X$  ULN on 2 or more consecutive blood tests
- patient discontinued from treatment due to a hepatic event or abnormality of liver tests
- hepatic event considered to be a SAE

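### AST counts towards considering discontinuation but does not prompt a repeat liver test, so a symptom-free, isolated AST above 5X and up to 8X ULN has no prompted second value

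*Protocol*

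**What the plan says.** Protocol Section 8.1.1 lists seven liver-test conditions under which stopping study drug should be "considered by the investigator when a patient meets one of the following conditions after consultation with the Lilly-designated medical monitor". Four of them name AST beside ALT: above 8X ULN; "ALT or AST >5X ULN for more than 2 weeks"; a level above 3X ULN together with either TBL above 2X ULN or an INR above 1.5; and above 3X ULN with fatigue, nausea, vomiting, right upper-quadrant pain, fever, rash or eosinophilia above 5%. The other three concern ALP.

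Section 9.4.5.1 holds the confirmation rule. It starts on "elevated ALT $\geq 3X$ ULN, ALP $\geq 2X$ ULN, or elevated TBL $\geq 2X$ ULN, liver testing", with a link to Appendix 4, and testing "should be repeated within 3 to 5 days including ALT, AST, ALP, TBL, direct bilirubin, gamma-glutamyl transferase, and creatine kinase". If the abnormality persists or worsens, the investigator starts monitoring in consultation with the study medical monitor. The section then adds: "Monitoring of ALT, AST, TBL, and ALP should continue until levels normalize or return to approximate baseline levels". AST is therefore in the repeat panel and in the continued monitoring, but no AST level starts either.

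The list of conditions for extra hepatic eCRF data, in the same section, follows the same pattern. Its first item is "elevation of serum ALT to" at least 5X ULN on two or more consecutive tests. The other laboratory items are TBL and ALP.

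AST is part of the routine chemistry panel (Appendix 2). The Schedule of Activities places that panel on treatment at Weeks 12, 24, 40 and 52.

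**The concern.** Section 8.1.1 treats the two transaminases alike, while Section 9.4.5.1 acts on only one of them. This matters for the criterion that contains a duration. A rise lasting more than 2 weeks cannot be seen in a single sample, so the criterion can be applied only if something produces a later one.

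Take two patients, both with normal ALP and TBL. One has ALT at 3X ULN: the protocol asks for a repeat in 3 to 5 days and, if the rise persists, monitoring of ALT and AST until it settles. The other has AST at 6X and ALT at 2.5X ULN. That patient is closer to a stated criterion for considering discontinuation, yet the written triggers ask for nothing. If sites follow the triggers literally, the patient may stay on drug for months before the next scheduled AST. A rise that lasted several weeks and then resolved would never be recognised as having met the criterion.

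**Working it through.** The plan states no figure to reproduce. The check is one of logic, followed by the visit calendar.

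**Step 1: which profiles escape the repeat trigger.** The trigger does not fire when ALT <3X, ALP <2X and TBL <2X ULN. Under those limits:

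- no criterion can be met through ALT, since each needs ALT above 3X, 5X or 8X;
- no ALP criterion can be met, since each needs ALP above 2.5X or 3X;
- the transaminase-plus-bilirubin criterion cannot be met through TBL, since TBL above 2X would itself fire the trigger.

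Only isolated AST rises remain.

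**Step 2: which of the remaining AST criteria need a second value.**

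| AST criterion in Section 8.1.1 | Can it be judged on the first result? |
|---|---|
| Above 8X | Yes |
| Above 3X with listed symptoms or eosinophilia | Yes |
| Above 3X with TBL above 2X | Yes, and the TBL trigger fires anyway |
| Above 5X for more than 2 weeks | No |

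The affected profile is AST above 5X and up to 8X, ALT <3X, ALP <2X and TBL <2X, with no listed symptom and no eosinophilia.

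**Step 3: when the next scheduled AST arrives.** Panel weeks and visit windows come from the Schedule of Activities (±3 days at Weeks 12 and 24; ±7 days at Weeks 40 and 52). Gap = difference in weeks × 7, widened by the sum of the two windows.

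- Week 12 to 24: 12 × 7 = 84 days; 84 ± (3 + 3) = 78 to 90.
- Week 24 to 40: 16 × 7 = 112 days; 112 ± (3 + 7) = 102 to 122.
- Week 40 to 52: 12 × 7 = 84 days; 84 ± (7 + 7) = 70 to 98.

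Against the 14 days in the criterion, 84/14 = 6 and 112/14 = 8; with windows, 70/14 = 5.0 and 122/14 = 8.7. The clinic visits at Weeks 16, 20 and 32 fall inside these gaps but carry no chemistry panel.

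**Step 4: what an AST trigger would change.** With AST ≥3X ULN added, every profile from Step 2 would prompt a repeat in 3 to 5 days. If the rise persisted, the existing monitoring instruction would run until it resolved. That would show whether it outlasted 2 weeks.

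**The case against.** The best defence is that other text covers the case. Section 9.2 states: "Investigators must document their review of each laboratory safety report". It also makes the investigator follow serious, medically important or drug-related events until they resolve or stabilise. Section 9.2.2.9 calls for hepatic monitoring when liver markers are raised, which could be read to include AST. Appendix 4 offers a list of liver tests that contains AST. Section 8.1.1 lets the investigator stop drug for any clinically significant laboratory value.

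This makes a sensible retest likely, and it rules out saying that no second value would ever be obtained. It does not supply a rule. Section 9.2 leaves follow-up frequency to the investigator, and Section 9.2.2.9 refers back to Section 9.4.5.1. Appendix 4 describes tests that may be obtained, or may be required in consultation with the sponsor's physician. None gives an AST level or a retest time.

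A second defence is that ALT-led triggering is deliberate. Exclusion criterion [18] also uses ALT alone, and AST can rise from non-hepatic causes. That is a fair reason to prefer ALT, but it does not explain why Section 8.1.1 gives AST a criterion that needs serial values.

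A reader might infer more than the documents support:

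- *That every AST of 5X to 8X with low ALT, ALP and TBL is left uncovered.* Patients with a listed symptom or eosinophilia meet a criterion on one value, and Section 7.7.1 says nausea and vomiting were among the most common events on the study drug in Phase 2.
- *That INR must be added to the repeat panel.* The repeat instruction already cites Appendix 4, which lists INR.
- *That the pandemic extension sets the size.* Appendix 7 allows the last visit up to Week 60, so the final gap could reach 147 days (day 420 minus day 273). That needs the latest contingency visit and the earliest Week 40 visit together.

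**Conclusion.** The point holds in a narrow form. One of the four AST criteria in Section 8.1.1 depends on a second value that no stated rule prompts, for the profile in Step 2. The next scheduled on-treatment value comes 84 or 112 days later (70 to 122 with standard windows), which is 5.0 to 8.7 times the period in the criterion.

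These figures are gaps between panels, not a count of patients affected or harmed. The documents give no frequency for this AST pattern; that it is uncommon is an assumption. The conclusion also assumes that sites follow the triggers as written. The practical effect is limited, because the criteria call for judgment after consultation and an investigator may retest or stop drug at any time. AST values, planned and unplanned, still enter the shift table in SAP Section 6.13.2.12.3. No endpoint, sample size or type 1 error rate is affected. This is a cheap improvement to safety monitoring.

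**What to change.** In Protocol Section 9.4.5.1, change the first repeat trigger from ALT alone to *ALT or AST ≥3X ULN*, leaving the ALP and TBL triggers as they are. The AST cut-off mirrors the existing ALT one.

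Optionally, and for consistency only, change the first item of the hepatic eCRF list to *ALT or AST ≥5X ULN* on two or more consecutive tests. This adds data collection but does not produce the missing second value. Hepatic data are already collected when drug is stopped for liver tests or a hepatic event is serious.

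The cost is one wording change and a matching central-laboratory flag, since AST is already measured in every chemistry panel. The downside is a few extra repeat draws, some of them for AST rises that do not come from the liver. The creatine kinase already in the repeat panel helps to identify those.

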#### **Hepatic Safety Data Collection**

Additional safety data should be collected via the eCRF if 1 or more of the following conditions occur:

- elevation of serum ALT to  $\geq 5X$  ULN on 2 or more consecutive blood tests
- elevated serum TBL to  $\geq 2X$  ULN (except for cases of known Gilbert's syndrome)
- elevation of serum ALP to  $\geq 2X$  ULN on 2 or more consecutive blood tests
- patient discontinued from treatment due to a hepatic event or abnormality of liver tests
- hepatic event considered to be a SAE

